For values items, we found that patients would rate competing values (such as dying quickly or living as long as possible) very highly when asked as single items, leaving little variability in responses. When forced to choose on a visual analogue scale, however, we found that groups of patients would discriminate their preferences. In total, the values items included herein account for 53% of the variance in relevant patient values. This item will be used to assess value-concordance going forward.

[name]'s dissertation: In his doctoral dissertation,⁵⁸ [name] surveyed current defibrillator patients at the University of Colorado (with the guidance of [name] - PI) to conceptualize relationships between how patients learned about their ICDs, how well they understand benefits and risks associated with ICD therapy, and QOL. In addition to creating new ICD knowledge and informational media history measures, the data gathered in this project highlighted group-based differences in treatment knowledge and information-seeking behavior. When compared to their younger counterparts, the oldest patients in the sample (age >71.5) both used fewer forms of media to learn about their ICD (being particularly less likely to use online information) and scored lower on a treatment knowledge measure, as did participants who did not complete high school when compared to those with at least a college degree. Significant depression and anxiety were also highly prevalent in this sample of patients (58% and 39.5%, respectively), and depression illustrated high statistical collinearity in models predicting patients' QOL. [name] continues to analyze whether this association indicates that depression drives QOL among ICD patients to a greater extent than previously thought, and/or the possibility that depression mediates other factors' influence on QOL.

Hartford-sponsored symposium on older adults: In 2014, Drs. [name] and [name] received funding from the Hartford Foundation to host a multi-disciplinary symposium of researchers to discuss the practice and research agenda for older adults considering ICDs. The proceedings from this symposium highlighted many aspects of ICD research and practice, including the importance of SDM for ICDs.⁴⁹

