Reach: Reach is defined as the proportion of the target population who participate in the intervention. While this is a straightforward measure, defining the denominator of eligible patients is surprisingly difficult. We will assess the percentage of patients that both receive and remember reviewing the PtDAs. Representativeness will be assessed by comparing participants to those who opt out on a range of available demographics and clinical indicators (e.g., age, gender, comorbidities) from chart review. As we are only enrolling a subset of patients into the trial at each site, we will ask the staff delivering the PtDAs to maintain a log of intervention recipients. We will obtain a waiver of consent to calculate aggregate reach at each site among all patients receiving ICDs.

Effectiveness:

- Primary outcome: Decision quality is an essential element of the Ottawa Decision Support Framework (Figure 2), defined as “the extent to which the implemented decision reflects the considered preferences of a well-informed patient.”⁵⁵ Decision quality measures consist of two domains: knowledge and values.
 - Knowledge: Consistent with methods developed by Sepucha et al.,^{55,56} we have developed a knowledge measure. We will use this measure to test knowledge at baseline and at 1 months and 6 months.
 - Value-treatment concordance: We will calculate concordance between patients’ values and the treatment they choose according to the validated methods of Sepucha et al.^{55,56} We will measure this in two ways: 1) we will measure the values-clarity subscale of the decision conflict measure (test-retest reliability and Cronbach’s alpha > 0.78, correlated with knowledge, regret, and treatment discontinuance) and 2) we will explore the prevailing value trade-off between “living longer even if it means getting an invasive therapy” versus “not living as long and avoiding an invasive therapy” as this item was able to discriminate between groups.
- Secondary outcomes: Additionally, we will collect the following secondary outcomes:
 - IPDAS process measures: We will use seven questions based on key domains of decision process as outlined in the IPDAS background document. [name] used these questions in his prior survey and they had significant reliability (Cronbach’s alpha of 0.78).⁷⁴
 - Decision choice: We will use single item measures of decision predisposition, choice, and enactment. These questions have test-retest reliability of 0.9 and correlates with values.^{75,76}

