 - Self-efficacy: The ‘Decision Self-Efficacy Scale’ measures self-confidence or belief in one’s ability to make decisions, including participate in shared decision making.⁷⁷
 - Control Preferences: This is a 2 question measure of a patient’s opinion of their preferred and actual role in decision-making.⁷⁸
 - The Decision Conflict Scale (DCS): DCS is a 10-item instrument that measures decision quality and determines decisional uncertainty.⁷⁹ The DCS quantifies personal perception of: a) uncertainty in choosing options; b) modifiable factors contributing to uncertainty such as feeling uninformed, unclear about personal values, and unsupported in decision making, and c) effective decision making such as feeling the choice is informed and values-based, and expressing satisfaction with the choice. DCS reliability measures include test-retest correlation and Cronbach’s alpha coefficients exceeding 0.78-0.90^{30,74}. The DCS discriminates between groups who make and delay decisions.³⁰

- The Decision Regret Scale: Decision regret is a 5-item scale which measures regret with the decision making. It is a commonly used measure in decision aid trials and has good reliability (Cronbach's alpha of 0.82-0.91).^{30,74} It correlates with satisfaction, decision conflict, and QOL.⁸⁰
- The Patient Health Questionnaire-2 (PHQ-2): This comprises the first 2 items of the PHQ-9, inquires about the degree to which an individual has experienced depressed mood and anhedonia over the past two weeks.⁸¹
- The Generalized Anxiety Disorder Scale (GAD-2): In primary care patients, the Generalized Anxiety Disorder scale (GAD-7) had high sensitivity for detecting generalized anxiety disorder and panic disorder. The GAD-2 had high sensitivity and specificity for GAD and high specificity for panic disorder, social anxiety disorder, and post-traumatic stress disorder.⁸²
- ICD experiences: These will be questions developed and used previously to describe ICD-specific issues such as whether the participant has experienced a shock or complication and whether they have considered discussing their ICD in an advance directive or with a surrogate decision maker.

B. Description of Population to be Enrolled:

Inclusion Criteria:

1. The participants in the trial will be adult (age ≥18) patients who have been offered a primary prevention ICD for initial implant, reimplantation, or CRT with defibrillation. Primary prevention must be for heart failure.

Exclusion Criteria:

1. Under 18 years of age

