Stepped-wedge multicenter trial (Table 3): We considered three potential designs for this trial. A classic patient-level randomization is not possible since programs (rather than patients) are effectively the primary targets of intervention implementation. The traditional cluster randomized trial would be disadvantaged by the small number of sites. Therefore, we propose a multicenter trial that is randomized at the clinic-level for a phased rollout of the shared decision support intervention.^{42,84} A variant of the cluster trial design, the stepped-wedge trial design is a one-way crossover cluster trial where all the groups will receive the intervention, but the time of intervention is randomly ordered. It is a compelling choice of design when 1) one of the goals is to study intervention implementation, 2) the intervention is thought to be efficacious, 3) all sites wish to receive the intervention and continue its implementation after the trial if it is effective, and 4) contamination/diffusion of the intervention effects to other subjects is likely. The stepped-wedge design is more efficient in terms of statistical power when compared to the classical cluster randomized design because the impact of the intervention is estimated using both within and between cluster differences.

Table 5: Measures	Baseline Pre Decision	1 Month Post Decision	6 Months Post Decision
-------------------	-----------------------	-----------------------	------------------------

COVARIATES			
- Demographics (combined survey and short chart review)	X		
- Medications, Comorbidities, Heart Failure Type/Severity	X		X
- Literacy (REALM-R 7 item) ⁸⁵ and Subjective Numeracy ⁸⁴	X		
EFFECTIVENESS OUTCOMES (see descriptions below)			
- Decision Quality – Knowledge	X	X	X
- Decision Quality – Value-concordance	X	X	X
- Decision Process		X	X
- Decision choice		X	X
- Self-Efficacy Scale	X	X	X
- Control Preferences	X	X	X
- Decision conflict	X	X	X
- Decision regret		X	X
- PHQ-2	X		X
- GAD-2	X		X
- ICD Experiences (+/- shock; +/- complications etc.)		X	X

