- Modular design: The sectional build of the PtDAs—clearly defined pages for the pamphlet and segmented video—allows for simple revision as problems are identified or information changes over time.

F. Data Analysis Plan:

Quantitative analysis (Hypotheses 1a, 1b, 1c): The analyses of the effectiveness will use a repeated measures mixed model. This strategy allows for partially incomplete data (e.g. missing follow-up or one of the collection periods) and relaxes the missing data assumptions to missing at

random conditional on observed data. Prior to these analyses, we will contrast the participants in the 2 phases of the study, identifying any patient/site characteristics that are unbalanced. If more than 3-5 variables are identified, we will develop a propensity score for the likelihood of being in the intervention phase. Each analysis model will include an indicator variable for the intervention phase, indicators for each of the sites and the variables identified above.

Sample Size and Power Calculation: This trial was designed to have diversity in implementation settings. As such, to effectively be powered to explore implementation across diverse settings, we are overpowered to test our primary quantitative outcomes (the knowledge domain of decision quality). With a sample size of 900 patients and a standard deviation of 18%, achieved power would approach 1.00 to detect a 10% improvement in knowledge (in the 2011 Cochrane Review, knowledge improved an average of 13.8%, in our pilot trial, knowledge improved 12%).⁶ Even with variance inflation for correlation within sites (assuming intraclass correlation 0.01), the power remains good at 0.98. This level of power will afford the ability to assess some heterogeneity of effect across sites and vulnerable patient groups, as well as adequate assessment of secondary effectiveness measures and implementation evaluation. To test the hypothesis that better informed patients will have less anxiety (hypothesis 1c), we will correlate the knowledge score with the HADS- A. Using a Pearson's correlation coefficient, for a sample size of 300 (based on 1/3 illustrating significant anxiety) then the person's correlation is 0.18 for a power of 90% and an alpha of 0.05.

G. Summarize Knowledge to be Gained:

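### The anxiety test for hypothesis 1c names HADS-A, which the trial does not schedule, and is sized on an expected anxious third (n=300) although 1c concerns all patients

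*Combined protocol and SAP*

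**What the plan says.** **The test.** In Section IV.F, the Sample Size and Power Calculation paragraph states how the anxiety part of 1c will be tested: "we will correlate the knowledge score with the HADS- A", using a Pearson coefficient. It gives a detectable correlation of 0.18 at 90% power and alpha 0.05, "for a sample size of 300 (based on 1/3 illustrating significant anxiety)". Sidedness is not stated, and neither are the visits from which the two scores are taken.

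**The instrument.** In Section IV.A the anxiety entry among the secondary outcomes is "The Generalized Anxiety Disorder Scale (GAD-2): In primary care patients" and so on; no HADS entry appears. Table 5 (Section IV.C), under "EFFECTIVENESS OUTCOMES (see descriptions below)", schedules GAD-2 at baseline and 6 months and has no HADS row. HADS is mentioned nowhere else in the text available for review, including the reference list.

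**The knowledge score.** Section IV.A says "We will use this measure to test knowledge at baseline and at 1 months and 6 months".

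**The hypothesis.** Hypothesis 1c in Section I, and row 1c of Table 1, speak of better-informed patients in general. Neither limits the claim to patients with anxiety.

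**The concern.** Two things do not fit together. First, the scale named for the test is not one the trial schedules. Second, the sample size is that of an expected anxious subgroup, while the hypothesis is about everyone enrolled. A correlation between two scores uses the full range of both, so the proportion above an anxiety cut-off has no place in sizing it. The available text also gives no such cut-off.

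How much this matters depends on what the 300 was meant to be. If it is only a cautious planning figure, the protocol understates what the trial can detect and nothing else changes. If it is the intended analysis set, patients would be selected on the outcome itself. That narrows the range of anxiety scores, weakens the correlation being sought, and answers a different question from the one in 1c. The text does not say which is meant.

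A smaller gap is that knowledge has three visits and GAD-2 has two, and the pair to be correlated is not named.

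**Working it through.** **Inputs.** From Section IV.F: 900 patients planned, n=300 for this test (900 × 1/3), detectable r = 0.18, power 90%, alpha 0.05. Assumptions here: a two-sided test; 10% to 30% of patients lacking one of the two scores (the documents give no figure for this); and, for step 3 only, bivariate normal scores.

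**Step 1. Reproduce the stated figure.** By Fisher's z, detectable r = tanh[(1.960 + 1.2816)/√(n − 3)] = tanh[3.2415/√(n − 3)].

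- n=300: tanh(3.2415/17.234) = tanh(0.1881) = 0.186.
- Power at r = 0.18: Φ(atanh(0.18) × 17.234 − 1.960) = Φ(3.136 − 1.960) = Φ(1.176) = 0.88.

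The stated 0.18 is therefore close (0.186 detectable; 88% rather than 90% power). A one-sided test would give 0.168. The arithmetic is not the fault; the basis for n is.

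**Step 2. If all patients with both scores are analysed.** Same formula:

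| Patients with both scores | n | Detectable r |
|---|---|---|
| All | 900 | 0.108 |
| 10% missing (assumed) | 810 | 0.114 |
| 20% missing (assumed) | 720 | 0.120 |
| 30% missing (assumed) | 630 | 0.129 |

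Power for r = 0.18 is above 0.99 in every row. On this reading n=300 is conservative.

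**Step 3. If only the most anxious third were analysed.** Suppose r = 0.18 among all patients, and keep the top fraction p = 1/3 on anxiety.

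- Cut-point: c = Φ⁻¹(2/3) = 0.431.
- Mean of anxiety above the cut, in SD units: λ = φ(c)/p = 0.3636/0.3333 = 1.091.
- Variance of anxiety above the cut: v = 1 + cλ − λ² = 1 + 0.470 − 1.190 = 0.280.
- Correlation inside the third: r√v/√(1 − r² + r²v) = (0.18 × 0.529)/√(1 − 0.0324 + 0.0091) = 0.0952/0.988 = 0.096.
- Power at n=300: Φ(atanh(0.0964) × 17.234 − 1.960) = Φ(1.666 − 1.960) = Φ(−0.294) = 0.38.

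The loss comes from two sources: fewer patients and a narrower range of anxiety. The 0.88 in step 1 does not describe this analysis, because it takes the correlation of 0.18 to hold within the 300.

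**The case against.** The best defence is that this is a slip in one sentence. GAD-2 is the only anxiety scale scheduled and the obvious substitute. The protocol never says the analysis is confined to anxious patients, and if all are analysed the calculation errs on the safe side. All of that stands, and it keeps the point modest. It does not make the sentence usable: the named variable will not exist, and the analysis set and visits remain to be chosen.

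A reader might go further in three ways that the documents do not support.

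- **That the protocol plans to analyse only anxious patients.** It does not say so. The 300 is given as a sample size with a rationale, not as an analysis population. The power of 0.38 is conditional on that reading.
- **That the stated 0.18 would distort how a null result is read.** A planning-stage detectable correlation is not a decision threshold. The test and its confidence interval will use the patients actually analysed.
- **That the Pearson correlation contradicts the mixed model.** The same section, under a heading that lists 1a, 1b and 1c, says "The analyses of the effectiveness will use a repeated measures mixed model" and "Each analysis model will include an indicator variable for the intervention phase, indicators for each of the sites and the variables identified above". Table 5 also groups GAD-2 with the effectiveness outcomes. But the sample-size paragraph expressly names the correlation as the test of the anxiety part of 1c, and Table 1 labels 1c as downstream effects rather than effectiveness. Taking the specific sentence to govern resolves most of the tension. Preferring an adjusted model is a choice, not the correction of an error.

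**Conclusion.** The point holds on two counts: the named instrument is not scheduled, and the basis for n=300 does not match the hypothesis. The test cannot be carried out as worded.

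If all patients are analysed, the consequence is only that sensitivity is understated: 0.108 at n=900, or 0.114 to 0.129 with an assumed 10% to 30% lacking paired scores, against the stated 0.18. The analysis itself is unaffected. If the anxious third were analysed, power for an overall correlation of 0.18 would be about 0.38 rather than the intended 0.90, given bivariate normal scores.

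The figures for all patients are normal-theory approximations for a simple correlation. They make no allowance for clustering by site or for GAD-2 being a short, coarse scale. Anxiety is a secondary outcome, and the primary knowledge comparison does not depend on any of this. It should be fixed, as a wording correction.

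**What to change.** In the Sample Size and Power Calculation paragraph of Section IV.F:

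1. Replace HADS-A with GAD-2 at 6 months, and name the one post-decision knowledge score (1 month or 6 months) to be correlated with it.
2. State that all enrolled patients with both scores are analysed.
3. Delete the one-third basis for n.
4. Restate the correlation detectable with 90% power at two-sided 0.05 as about 0.11 at n=900, or about 0.12 at n=720 under an assumed 20% loss. Label these as approximate normal-theory figures for a simple correlation, before clustering and for a short, coarse scale.

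Adjusting for site and baseline GAD-2 is optional; both are already recorded.

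The cost is wording only. Knowledge and GAD-2 are already scheduled at the visits needed, so no new data or patients are required.
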